APPENDIX 1 DIAGNOSTIC CRITERIA FOR DRUG AND ALCOHOL ABUSE

The following is taken from DSM-IV:

Diagnostic Criteria for Psychoactive Substance Dependence

A maladaptive pattern of substance use, leading to clinically significant impairment or distress as manifested by three (or more) of the following, occurring at any time in the same 12-month period:

1. Tolerance, as defined by either of the following:
 - a) A need for markedly increased amounts of the substance to achieve intoxication or desired effect,
 - b) Markedly diminished effect with continued use of the same amount of the substance.
2. Withdrawal, as manifested by either of the following:
 - a) The characteristic withdrawal syndrome for the substance,
 - b) The same (or closely related) substance is taken to relieve or avoid withdrawal symptoms.
3. The substance is often taken in larger amounts or over a longer period than was intended.
4. There is a persistent desire or unsuccessful efforts to cut down or control substance use.
5. A great deal of time is spent in activities necessary to obtain the substance (e.g., visiting multiple doctors or driving long distances), use the substance (e.g., chain-smoking) or recover from its effects.
6. Important social, occupational or recreational activities are given up or reduced because of substance use.
7. The substance use is continued despite knowledge of having a persistent or recurring physical or psychological problem that is likely to have been caused or exacerbated by the substance (e.g., current cocaine use despite recognition of cocaine-induced depression, or continued drinking despite recognition that an ulcer was made worse by alcohol consumption.)

Criteria for Severity of Psychoactive Substance Dependence:

Mild: Few, if any, symptoms in excess of those required to make the diagnosis, and the symptoms result in no more than mild impairment in occupational functioning or in usual social activities or relationships with others.

Moderate: Symptoms or functional impairment between “mild” and “severe”.

Severe: Many symptoms in excess of those required to make the diagnosis, and the symptoms markedly interfere with occupational functioning or with usual social activities or relationships with others.

In Partial Remission: During the past six months, some use of the substance and some symptoms of dependence.

In Full Remission: During the past six months, either no use of the substance, or use of the substance and no symptoms of dependence.

Diagnostic Criteria for Psychoactive Substance Abuse

- A. A maladaptive pattern of psychoactive substance use, leading to clinically significant impairment or distress as manifested by one (or more) of the following, occurring at any time in the same 12-month period:
1. Recurrent substance use resulting in a failure to fulfill major role obligations at work, school, or home (e.g., repeated absences or poor work performance related to substance use; substance-related absences, suspensions, or expulsions from school, neglect of children or household).
 2. Recurrent substance use in situations in which it is physically hazardous (e.g., driving an automobile or operating a machine when impaired by substance use).
 3. Recurrent substance-related legal problems (e.g., arrests for substance-related disorderly conduct).
 4. Continued substance use despite having persistent or recurrent social or interpersonal problems caused or exacerbated by the effects of the substance (e.g., arguments with spouse about consequences of intoxication, physical fights).
- B. The symptoms have never met the criteria for substance dependence for this class of substance.

Official Title of Study:

A RANDOMIZED, DOUBLE-BLIND, PLACEBO-CONTROLLED, PARALLEL-GROUP,
MULTIPLE DOSE STUDY TO EVALUATE THE SAFETY, PHARMACOKINETICS
AND PHARMACODYNAMIC EFFECTS OF BMS-986036 IN ADULTS WITH NONALCOHOLIC
STEATOHEPATITIS

NCT Number: NCT03400163

Document Date (Date in which document was last revised): September 18, 2017

**STATISTICAL ANALYSIS PLAN
FOR MB130045**

**A RANDOMIZED, DOUBLE-BLIND, PLACEBO-CONTROLLED, PARALLEL-GROUP,
MULTIPLE DOSE STUDY TO EVALUATE THE SAFETY, PHARMACOKINETICS
AND PHARMACODYNAMIC EFFECTS OF BMS-986036 IN ADULTS WITH NON-
ALCOHOLIC STEATOHEPATITIS**

VERSION # 2.0

TABLE OF CONTENTS

STATISTICAL ANALYSIS PLAN FOR MB130045	1
TABLE OF CONTENTS	2
LIST OF TABLES	4
[REDACTED]	
2 STUDY DESCRIPTION	7
2.1 Study Design	7
2.2 Treatment Assignment	8
2.3 Blinding and Unblinding	9
2.3.1 Interim Analysis Unblinding	10
2.4 Protocol Amendments	10
3 OBJECTIVES	10
3.1 Primary Objectives	10
3.2 Secondary Objectives	10
[REDACTED]	
4 ENDPOINTS	11
4.1 Efficacy Endpoints	11
4.2 Safety Endpoints	11
4.3 Pharmacokinetic Endpoints	11
4.4 Immunogenicity Endpoints	11
[REDACTED]	
5 SAMPLE SIZE AND POWER	12
6 STUDY PERIODS, TREATMENT REGIMENS AND POPULATIONS FOR ANALYSES	12
6.1 Study Periods	12
6.2 Treatment Regimens	12
6.3 Populations for Analyses	13
7 STATISTICAL ANALYSES	13
7.1 General Methods	14
7.2 Study Conduct	14
7.3 Study Population	14
7.3.1 Subject Disposition	14
7.3.2 Demographic Characteristics	14

LIST OF TABLES

Table 2.1-1: Study Design Schematic 8
Table 6.2-1: Treatment Administration..... 13
Table 7.6.5-1: Criteria for ECG Results Outside of a Pre-specified Range 19
Table 7.6.6-1: Criteria for Vital Signs Results Outside of a Pre-specified Range 19

Research Hypothesis:

BMS-986036 administered daily or weekly for 16 weeks to obese adults with NASH will lower hepatic fat fraction (%) assessed by MRI to a greater extent than placebo.

Schedule of Analyses:

When approximately 60 subjects have completed 8 weeks of treatment, an interim analysis will be performed. Analyses will consist of summaries of the available data without revealing individual subjects' treatment assignments. The results of the interim analysis will be reviewed by a pre-specified panel of personnel.

Primary Analysis will be performed following the database lock after all subjects complete the end of treatment. Final analysis will be performed following the data base lock after all subjects have completed the study.

2 STUDY DESCRIPTION

2.1 Study Design

Study MB130045 is a randomized, double-blind, placebo-controlled, parallel-group, multiple dose design. Subjects will undergo screening evaluations to determine eligibility within 42 days prior to randomization. There will be a 7-day study skills training (Lead-In) period prior to randomization on Day 1. Eligible subjects will be randomized via Interaction Voice Response System (IVRS) on Day 1 to 1 of 3 parallel treatment groups. In total, approximately 90 randomized subjects (30 per group; ratio 1:1:1) will self-administer double-blind treatment, once daily for 16 weeks, in an outpatient setting. Subjects will be stratified using diagnosis of Type 2 diabetes mellitus (yes vs no) based on current American Diabetes Association criteria. Clinic visits are scheduled approximately every 2 weeks initially, and then monthly, to collect safety, PK and PD measures. The study design schematic is presented in [Table 2.1-1](#):

For each subject, the total scheduled study duration from Screening to last Follow-up visit is approximately 12 months, comprised of screening (Day -42 to Day -8), placebo lead-in (approximately Day -7 to Day -1), on-treatment (Day 1 to Day 112) and a wash-out follow-up (Day 113 to Day 142) period, plus a scheduled follow-up visit that will be performed approximately 6 months (Day 292) after the last dose to perform DXA scanning and an additional immunogenicity measurement. Of note, subjects with a positive result in the ADA and/or anti-FGF21 antibody assays at the Day 142 and/or Day 292 follow-up visits, and who do not have evidence of decreasing or stable antibodies, will be followed for up to 12 months after the D142 visit until antibody levels resolve or demonstrate a consistent decreasing trend (these immunogenicity follow-up visits will be conducted approximately every 6-8 weeks).

The end of the study is defined as the date of the last scheduled follow-up visit, or immunogenicity follow-up visit, whichever is later, of the last subject in the study.

Table 2.1-1: Study Design Schematic

Visit Days										
D -42 ^a	D -7	D 1	D 15	D 29	D 43	D 57	D 86 ^b	D 112 ^c	D 142	D 292 ^d
Screening 5 weeks	Lead-in 1 week	On treatment 4 months							Follow-up	
	Placebo	Treatment A: 10 mg QD (daily) Treatment B: 20 mg QW (weekly) Treatment C: Placebo QD								

^a MRI, MRE, and DXA baseline scans should be performed approximately 21 days prior to the Day 1 dose. Eligibility should be confirmed by central imaging lab prior to entry into the lead-in period (Day-7).

^b The Day 86 visit is scheduled 4 weeks +1 day after the Day 57 visit, to tie in with a PK assessment.

^c MRI, MRE and DXA end of treatment scans are conducted at Day 112 (+/- 1 week).

^d DXA follow-up scan and immunognoicity sample collection are conducted 6 months (+/- 2 weeks) after the last dose.

D = Day

2.2 Treatment Assignment

During the Screening visit, the investigative site will call into the enrollment option of the IVRS designated by BMS for assignment of a 5-digit subject number that will be unique across all sites. Enrolled subjects, including those not dosed, will be assigned sequential subject numbers starting with 00001, eg, 00001, 00002, 00003.... 00010. The patient identification number (PID) will ultimately be comprised of the site number and subject number. For example, the first subject screened (ie, enrolled) at site number 1, will have a PID of 0001 00001. Once it is determined that the subject meets the eligibility criteria following the Screening visit, the investigative site will call the IVRS to randomize the subject into the open dose panel.

At the time of entry into the lead-in period (Day -7 visit), the site will call IVRS in order for the lead-in medication to be assigned and dispensed. Subjects who successfully complete the lead-in period and meet the criteria for entry into the treatment period, will be randomly assigned by the IVRS to one of the following 3 double-blind treatment groups in a 1:1:1 ratio:

- BMS-986036 10 mg once daily (QD)
- BMS-986036 20 mg once weekly (QW)
- Placebo QD

Randomization will be stratified based upon diagnosis of Type 2 diabetes mellitus (yes vs. no).

The two strata for randomization are defined as follows:

- Strata 1: Diabetes Mellitus - Yes
- Strata 2: Diabetes Mellitus - No

Randomized subjects who discontinue will not be replaced.

Randomization schedules for both subject treatment and containers will be generated and kept by Bristol- Myers Squibb and stored in a secure location with restricted access.

At all study visits when study medication is dispensed, each subject will be assigned a kit number by the IVRS. Kit numbers will be assigned randomly and will correspond to the numbers printed on the packages and kits containing study drug. Kit numbers will be recorded on the appropriate eCRFs. The IVRS will be available 24 hours per day, 7 days per week.

2.3 Blinding and Unblinding

Blinding of treatment assignment is critical to the integrity of this clinical study. However, in the event of a medical emergency or pregnancy in an individual subject in which knowledge of the investigational product is critical to the subject's management, the blind for that subject may be broken by the investigator. The subject's safety takes priority over any other considerations in determining if a treatment assignment should be unblinded.

Before breaking the blind of an individual subject's treatment, the investigator should determine that the unblinded information is necessary, i.e., that it will alter the subject's immediate management. In many cases, particularly when the emergency is clearly not related to the investigational product, the problem may be properly managed by assuming that the subject is receiving active product. It is highly desirable that the decision to unblind treatment assignment be discussed with the Medical Monitor, but the investigator always has ultimate authority for the decision to unblind. The Principal Investigator should only call in for emergency unblinding AFTER the decision to discontinue the subject has been made.

In cases of accidental unblinding, contact the Medical Monitor and ensure every attempt is made to preserve the blind.

Any request to unblind a subject for non-emergency purposes should be discussed with the Medical Monitor.

In case of an emergency, the Investigator(s) has unrestricted access to randomization information via the IVRS and is capable of breaking the blind through the IVRS system without prior approval from sponsor. Following the unblinding the Investigator shall notify the Medical Monitor and/or Study Director.

Also, designated staff of BMS Research and Development can be unblinded at any time. The Bioanalytical Sciences section or its designate will be unblinded to the randomized treatment assignments in order to minimize unnecessary analysis of samples from control group subjects. A single pharmacokineticist or designate in Clinical Pharmacology Pharmacometrics and a Biomarker scientist may be unblinded in order to prepare preliminary summaries of

[REDACTED]

4 ENDPOINTS

4.1 Efficacy Endpoints

The primary efficacy endpoint is the change in hepatic fat fraction (%) by MRI from baseline to Week 16.

4.2 Safety Endpoints

The primary safety endpoints include incidence of AEs, serious AEs, and events of special interest including injection site assessment, AEs leading to discontinuation, and death as well as marked abnormalities in clinical laboratory tests, vital sign measurements, ECGs, physical examinations and bone mineral density (BMD) collected by DXA scan at specified time points in Table 5.1-1, Table 5.1-2 and Table 5.1-3 of the Protocol.

4.3 Pharmacokinetic Endpoints

The first secondary objective is to assess the pharmacokinetics of Total and C-Terminal intact BMS-986036 in NASH subjects. PK endpoints include C_{trough}.

4.4 Immunogenicity Endpoints

The second secondary objective to assess the effect of daily or weekly doses of BMS-986036 on immunogenicity in NASH subjects will be measured by anti-BMS-986036 antibodies and anti-FGF21 antibodies at the specified time points in Table 5.5.1-1 of the Protocol.

[REDACTED]

5 SAMPLE SIZE AND POWER

The primary objective is to compare the change in hepatic fat fraction (%) from baseline to week 16 between each of 2 doses of BMS-986036 treatment group and placebo treatment group. With 27 subjects per treatment group with post-baseline measurements, there will be 82% power to detect a difference of 5% in mean change from baseline at Week 16 in hepatic fat fraction (%) between each of 2 doses of BMS-986036 treatment groups (10 mg daily and 20 mg weekly) and placebo at a significance level of 0.05 (one-sided). These calculations are based on an assumption that the hepatic fat fraction (%) change from baseline is normally distributed with a standard deviation of no greater than 7%, as estimated from data reported in a similar population^{8,9}. No adjustment will be made for multiplicity.

To allow for dropouts, approximately 30 subjects per treatment group (total of 90 subjects) will need to be randomized, assuming up to 10% of the subjects do not complete post-baseline assessments.

6 STUDY PERIODS, TREATMENT REGIMENS AND POPULATIONS FOR ANALYSES

6.1 Study Periods

Screening: refers a period from the time the Informed Consent form is signed until initiation of the first lead-in placebo dose.

Lead in period: refers to a period from the first lead-in placebo dose until initiation of the first treatment dose.

On-Treatment period: refers to a period from the first treatment dose date to 14 days after the last treatment dose.

Follow-up period: refers to a period 15 days after the last treatment dose date.

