3.3.1 Inclusion Criteria

1. Signed Written Informed Consent

- a. Signed informed consent form.

2. Target Population

- a. Liver biopsy performed within 1 year of Screening or may be performed between Screening and Lead-in (Day -7) with documented results of NASH with NASH CRN fibrosis stage 1-3, or equivalent using a different scoring system.
- b. Body mass index (BMI) of ≥ 25 . Note: $BMI = \text{weight (kg)} / [\text{height (m)}]^2$
- c. Hepatic fat fraction (%) $\geq 10\%$ by MRI performed during the Screening period.
- d. Subject is able to medically tolerate the performance of the MRI or DXA scans and has suitable weight and circumference. See [Section 3.4.3](#) for further details.
- e. Subject agrees not to initiate a weight loss program and agrees to maintain consistent dietary habits and exercise regimen for the duration of the study.
- f. Subject re-enrollment: This study permits the re-enrollment of a subject that has discontinued the study as a pre-treatment failure (i.e., subject has not been randomized / has not been treated). If re-enrolled, the subject must be re-consented and will receive a new subject number.

3. Age and Reproductive Status

- a. Males and females, ages 21 to 75 years, inclusive
- b. Women of childbearing potential (WOCBP) must have a negative serum or urine pregnancy test (minimum sensitivity 25 IU/L or equivalent units of HCG) within 24 hours prior to the start of study drug.
- c. Women must not be breastfeeding.

- d. WOCBP must agree to follow instructions for method(s) of contraception for at least 4 weeks before dosing, for the duration of treatment with study drug (s) 16 weeks plus 5 half-lives of study drug (30 days) plus 30 days (duration of ovulatory cycle) for a total of 2 months post-treatment completion.
- e. Males who are sexually active with WOCBP must agree to follow instructions for method(s) of contraception for the duration of treatment with study drug (16 weeks) plus 5 half-lives of the study drug (30 days) plus 90 days (duration of sperm turnover) for a total of 4 months post-treatment completion.
- f. Azoospermic males and WOCBP who are continuously not heterosexually active are exempt from contraceptive requirements. However they must still undergo pregnancy testing as described in this section.

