Targeted PE		X	A targeted physical exam should be performed by the investigator or qualified professional. It includes assessment of heart, lung, abdomen and injection site reactions (as measured by the Draize Scale for erythema and edema (see Section 5.3.3) and should also be guided by the examiner's observations and/or patient complaints on new or changed conditions,

Table 5.1-1: Screening Procedural Outline (MB130045)

Procedure	Screening	Lead-in	Notes
	D-42 to D-8	D-7	
			symptoms or concerns.
Physical Measurements	X	X	Weight, BMI and waist circumference measurement. See Section 5.9 Height at screening only.
Vital Signs	X		Includes body temperature, respiratory rate, seated blood pressure and heart rate. Blood pressure and heart rate should be measured after the subject has been seated quietly for at least 5 minutes.
Electrocardiogram (ECGs)	X		ECGs should be recorded after the subject has been supine for at least 5 minutes. ECG parameters including QTcF will be collected on the CRF.
IVRS Call	X	X	IVRS call to be conducted on the day of each subject visit where indicated
Laboratory Tests (hematology, clinical chemistry, urinalysis, INR)	X		Subjects are required to fast for at least 10 hours prior to the collection of specimens for clinical laboratory tests.
Pregnancy Testing	X		Female subjects of child bearing potential. Serum pregnancy testing performed at screening
██████████	█		
Lipid panel	X		Triglycerides, total cholesterol, LDL and HDL
FSH	X		In women <55 years, to confirm menopause.
Clinical Drug Supplies			
Dispense Lead-in supply		X	
Review injection technique		X	
Adverse Event Reporting			
Monitor for Non-Serious Adverse Events		X	All non-serious AEs will be collected from the start of the Lead-In phase until 30 days after discontinuation of dosing. AEs should be followed to resolution or stabilization.
Monitor for Serious Adverse Events	X	X	All SAEs must be collected from the date of subject's written consent until 30 days after discontinuation of dosing. In addition, the investigator should report any SAE that occurs after 30 days post-dosing that is believed to be related to study drug or protocol-specified procedure

Abbreviations: D = Day

Table 5.1-2: On Treatment Procedural Outline (MB130045)

Procedure	D 1	D 15	D 29	D 43	D 57	D 86	End of Treatment D 112	Early Termination Visit ^a	Notes
Clinic Visit Window (days)	0	+3	+3	+3	+3	+3	-3		

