Patient diary review	X	X	X	X	X	X	X	X	
^a Early Termination is not a scheduled visit. For early termination PK and PD assessments, refer to Table 5.5.1-1 Abbreviations: D = Day									

Table 5.1-3: Post Treatment Follow-up Procedural Outline (MB130045)

Procedure	D 142 (30 days after last dose)	D 292 (6 mo after last dose)	Follow-up for immunogenicity ^a (up to 12 months post Day 142)	Early Termination Visit ^b	Notes
Visit Window	+/- 3 days	+/-2 wk	n/a		
IVRS Call	X			X	
Safety Assessments					
Physical Examination	X			X	
Targeted Physical Examination					Injection site reactions (as measured by the Draize Scale for erythema and edema (see Section 5.3.3), others as clinically indicated. See note in Screening procedures.
Physical Measurements	X			X	Weight (using calibrated scale), BMI and waist circumference measurement.
Vital Signs	X			X	See note in screening procedures.
Electrocardiograms (ECGs)	X			X	See note in screening procedures.
Laboratory Tests (hematology, clinical chemistry, urinalysis, INR)	X			X	See note in screening procedures.
Pregnancy Testing	X			X	Female subjects of child-bearing potential. Urine pregnancy testing to be performed at post treatment specified visits with reflex to serum if urine pregnancy testing is positive.
Dual-emission X-ray Absorptiometry (DXA)		X			Bone imaging (hip and lumbar spine) at all imaging facilities.
Adverse Event Reporting					
Monitor for Adverse Events	X			X	Up to 30 days after the last dose.
Monitor for Serious Adverse Events	X			X	See note in screening procedures.
Pharmacokinetic (PK) Assessments					
PK Sampling	X	X			Refer to Table 5.5.1-1
Immunogenicity testing	X	X	X	X	Refer to Table 5.5.1-1 and Section 5.7
████████████████████	██████████				
██████████	██████████				

^a Applies only to subjects with positive immunogenicity at D142 and/or D292. (Refer to [Section 5.7](#)). These immunogenicity follow-up visits will commence after D142 or D292, if immunogenicity results are positive at D142 or D292, respectively, without evidence of decreasing or stable antibodies.

^b Early Termination is not a scheduled visit. For early termination PK and PD assessments, refer to [Table 5.5.1-1](#)

Abbreviations: D = Day

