6.4 Pregnancy

If following initiation of the investigational product, it is subsequently discovered that a study subject is pregnant or may have been pregnant at the time of study exposure, including during at least 5 half lives after product administration, the investigator must immediately notify the BMS Medical Monitor/designee of this event and complete and forward a Pregnancy Surveillance Form to BMS Designee within 24 hours and in accordance with SAE reporting procedures described in [Section 6.1.1](#).

In most cases, the study drug will be permanently discontinued in an appropriate manner (e.g., dose tapering if necessary for subject safety).

In the rare event that the benefit of continuing study drug is thought to outweigh the risk, after consultation with BMS, the pregnant subject may continue study drug after a thorough discussion of benefits and risk with the subject.

Protocol-required procedures for study discontinuation and follow-up must be performed on the subject unless contraindicated by pregnancy (e.g., x-ray studies). Other appropriate pregnancy follow-up procedures should be considered if indicated.

The investigator must immediately notify the BMS (or designee) Medical Monitor of this event and complete and forward a Pregnancy Surveillance Form to BMS (or designee) within 24 hours and in accordance with SAE reporting procedures described in [Section 6.1.1](#).

Follow-up information regarding the course of the pregnancy, including perinatal and neonatal outcome and, where applicable, offspring information must be reported on the Pregnancy Surveillance Form.

Any pregnancy that occurs in a female partner of a male study participant should be reported to BMS. Information on this pregnancy will be collected on the Pregnancy Surveillance Form.

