7.6.4 Clinical Laboratory Evaluations

The results of all protocol-specified clinical laboratory tests, as well as laboratory results outside of the normal range, will be listed for all treated subjects. Scheduled laboratory measurements and corresponding change from baseline values will be summarized by treatment and nominal visit for each laboratory test. Laboratory abnormalities are determined from laboratory measurements analyzed at the central or local laboratory, and are graded using the Division of AIDS (DAIDS) Table for Grading the Severity of Adult and Pediatric Adverse Events.¹¹

For each laboratory test, emergent laboratory abnormalities (not emergent, grade 1, grade 2, grade 3, grade 4, grade 1 to 4; grade 3 to 4) are summarized by treatment for all treated subjects. On-treatment emergent abnormalities are those with a higher toxicity grade than the baseline toxicity grade (including missing baseline). Laboratory abnormalities regardless of baseline toxicity grade are also summarized analogously by treatment. Commonly collected laboratory tests with DAIDS toxicity grades may include the following: hemoglobin, leukocytes, lymphocytes (absolute), neutrophils + bands (absolute), platelet, ALT, AST, total bilirubin, Direct bilirubin, alkaline phosphatase, GGT, albumin, INR, creatinine, calcium, phosphorus, magnesium, fasting glucose.

Laboratory abnormalities on treatment are also summarized by baseline toxicity grade (grade 0; grade 1, grade 2; grade 3, grade 4) and treatment regimen for the following laboratory tests: ALT, AST, total bilirubin, direct bilirubin, alkaline phosphatase, calcium.

The laboratory value during the study period with the highest toxicity grade is reported for each test.

Laboratory results for subjects with any laboratory abnormality with grade 3 and grade 4 (scheduled and unscheduled) will be listed.

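### SAP 6.1 closes the on-treatment period 14 days after the last dose, so the Day 142 laboratory draw drops out of the by-arm emergent-abnormality tables in SAP 7.6.4

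*SAP*

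**What the plan says.** SAP 6.1 defines the period as "On-Treatment period: refers to a period from the first treatment dose date to 14 days after the last treatment dose", and the next one as "Follow-up period: refers to a period 15 days after the last treatment dose date". It gives no reason for 14 days.

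SAP 7.6.4 summarises emergent laboratory abnormalities by treatment for all treated subjects and defines them as follows: "On-treatment emergent abnormalities are those with a higher toxicity grade than the baseline toxicity grade". A second table, by baseline grade, is limited to abnormalities on treatment and covers ALT, AST, total and direct bilirubin, alkaline phosphatase and calcium. The section states no time window of its own for either table. It also plans listings of all results, a listing for subjects with Grade 3 or 4 abnormalities, and summaries by nominal visit.

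SAP 7.6.3 tabulates adverse events from the first active dose onward, with no closing date.

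Protocol Table 5.1-3 labels the first follow-up visit "D 142 (30 days after last dose", with a window of 3 days either side. The full safety panel is marked at that visit and not at Day 292. The adverse event row in the same table carries the note "Up to 30 days after the last dose". Protocol 3.3.1, in the contraception criteria, writes "plus 5 half-lives of study drug (30 days".

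**The concern.** Laboratory abnormalities are part of the primary safety endpoint (Protocol 8.3.1, SAP 4.2), and both sections point to the schedule tables, including the post-treatment one. In a population with liver disease, the proportion of subjects per arm with a new or higher grade is a natural summary to read. If the SAP 6.1 period governs, a grade increase first seen at Day 142 is missing from that proportion and from the baseline-grade table for the liver tests.

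The two safety domains also run over different windows. A Day 142 abnormality that the investigator reports as an adverse event enters the adverse event table but not the emergent laboratory table of the same report. The 14-day limit matches no period in the protocol: Protocol 3.1 (repeated in SAP 2.1) ends on-treatment at Day 112 and runs wash-out follow-up to Day 142.

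**Working it through.** **Inputs**
- End of dosing: Day 112, with a clinic window of up to 3 days early (Protocol Table 5.1-2), so Days 109 to 112.
- On-treatment cut-off: last dose + 14 days (SAP 6.1).
- Follow-up draw: Day 142, plus or minus 3 days (Protocol Table 5.1-3).
- 5 half-lives = 30 days (Protocol 3.3.1).
- Scheduled laboratory draws after Day 1: Days 15, 29, 43, 57, 86 and 112 on treatment (Table 5.1-2), then Day 142 (Table 5.1-3).

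**Reproducing the protocol's figure.** 142 - 112 = 30 days, which agrees with the Day 142 column label.

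**Where the draw falls**
- Visit window: 142 - 3 = Day 139 to 142 + 3 = Day 145.
- Last dose Day 112: cut-off 112 + 14 = Day 126. The gap is 139 - 126 = 13 to 145 - 126 = 19 days.
- Last dose Day 109: cut-off 109 + 14 = Day 123. The gap is 139 - 123 = 16 to 145 - 123 = 22 days.
- To count as on-treatment, the earliest in-window visit would need a last dose on Day 139 - 14 = Day 125 or later, which is beyond planned dosing. No in-window Day 142 draw of a completer can enter.
- Draws counted: 6 of 7 scheduled after baseline.

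**In half-lives**
- Implied half-life: 30 / 5 = 6 days.
- The SAP cut-off: 14 / 6 = 2.3 half-lives.
- Fraction of drug left at Day 142: 0.5^(30/6) = 0.5^5 = 0.031, about 3%. Over the visit window after a Day 112 dose (27 to 33 days) it runs from 0.5^4.5 = 0.044 to 0.5^5.5 = 0.022.

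**What a plain 30-day cut-off would do**
- Last dose Day 112: period ends on Day 142, so in-window visits on Days 143 to 145 are still missed. Capturing Day 145 needs 145 - 112 = 33 days.
- Last dose Day 109 with the visit held to the study day: 145 - 109 = 36 days are needed.
- The rule therefore has to name the visit as well as the number of days.

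**The case against.** A reader might infer that the protocol sets 30 days as the exposure window for safety analysis and that the SAP contradicts it. The documents do not support that. The half-life figure belongs to the contraception criteria. The wording "at the time of study exposure, including during at least 5 half lives after product administration" belongs to pregnancy reporting. The statement "All non-serious AEs will be collected from the start of the Lead-In phase until 30 days after discontinuation of dosing" sets a collection period, and collection and analysis periods need not be equal. Both documents call Days 113 to 142 wash-out, and last dose + 14 days is wider than the protocol's own on-treatment period.

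A reader might also size the problem by the drug still present at day 14, 0.5^(14/6) = about 20%, or by the share of the 30 days left out, (30 - 14)/30 = 53%. Neither describes missing laboratory data, because completers have no scheduled draw between Day 112 and Day 142. At the draw that is affected, about 3% of drug remains.

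Nor are the data lost. Day 142 values appear in the listings and the nominal-visit summaries, and clinically significant abnormalities must be recorded as adverse events (Protocol 5.3.2 and 6.3), whose tables have no cut-off. These points stand and limit the harm. But visit-level means and listings do not give the proportion of subjects per arm with an emergent abnormality.

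Finally, the exclusion is a reading of the text. SAP 7.6.4 does not cite SAP 6.1, its worst-grade rule refers to the study period without defining it, and SAP 7.6 and 8 defer to sponsor guidance and conventions that are not reproduced. If those documents set a wider window, the tables may already include Day 142. The SAP should then say so.

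**Conclusion.** The point holds as a modest gap in the laboratory safety tables, not as a conflict with a protocol-defined exposure window. As written, the emergent and baseline-grade tables leave out one scheduled draw for every completer, in a trial of about 90 subjects. What they miss is a grade that is new or higher for the first time at that draw; abnormalities already graded as high on treatment are counted anyway. The documents give no rate from which to estimate how many such cases there would be.

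The calendar result rests on the scheduled days and windows and on reading on-treatment in SAP 7.6.4 as the period in SAP 6.1. It does not depend on the half-life. The 6-day half-life is implied by the protocol's contraception figure and is not a reported pharmacokinetic estimate; if 30 days was rounded up, less drug remains at Day 142. The efficacy analysis and the adverse event tables are unaffected.

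**What to change.** In SAP 7.6.4, state that emergent abnormalities and abnormalities by baseline grade are counted from the first double-blind dose to 30 days after the last dose or through the Day 142 visit, whichever is later. State the window for the remaining laboratory tables too, including the one that ignores baseline grade and the worst-grade rule. The 14-day version may be kept alongside, with a reason for choosing 14 days.

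Do not put an end date on the adverse event tables for the sake of uniformity. Protocol 6.1.1 asks for serious events believed related to study drug to be reported after the 30-day period, and a common cut-off could drop them from the by-arm tables.

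The cost is SAP wording and one date cut-off in programming; no visit or sample changes. The downside is that some laboratory values taken after most drug has cleared will count as treatment-emergent, which showing both windows would make visible.
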